### 20.3 Appendix 3: Mitigation of Side Effects

- All side effects will be recorded as AEs or SAEs and reported accordingly
- AE and SAE will be inquired about in both phone conversations and in the Subject Diary
- Auditory
  - Tinnitus and deafness
    - Subjects experiencing either of these symptoms will be referred to their primary care physician for treatment.
- Dermatological
  - Rash or pruritis, including Vesiculobullous rash or Maculopapular rash
    - Subject will be prescribed appropriate treatment depending on the type of rash or pruritis
  - Photosensitivity reaction
    - Subject will be advised to avoid sunlight for the duration of treatment. If Subject must go out, they should wear pants and long sleeves.
  - Stevens-Johnson syndrome, DRESS syndrome, TEN
    - Subject will be referred to a hospital for evaluation treatment
  - Urticaria
    - Will be treated with antihistamines and observed. If this treatment is not effective, the Subject will be re-evaluated by PI for further treatment and/or referral
  - Dermatitis including exfoliative dermatitis
    - Subject will be evaluated by the PI and treatment will be initiated based on the type of dermatitis. Therapies could include topical hydrocortisone cream, antihistamines, and glucocorticoids
  - Dry Skin
    - Subject will be provided with a skin care recommendation depending on the degree of severity
  - Hyperhidrosis
    - Subject will be referred to their PCP for evaluation
  - Eczema
    - Subject will be provided with topical treatment if necessary
  - Erythema multiforme
    - Subject will be observed, as this condition usually resolves without treatment. The efficacy of glucocorticoids in this condition is debated
  - Fungal dermatitis
    - Subject will be prescribed appropriate antifungal medication
  - Pigmentary changes in skin and mucous membranes
    - Usually reversible upon discontinuation of medication
  - Bleaching of hair
    - Usually reversible upon discontinuation of medication
  - Alopecia
    - If severe, medication may be discontinued. This condition is usually reversible upon discontinuation of medication
  - AGEP
    - Usually reversible upon discontinuation of medication
  - Outbreak of psoriasis, occasionally associated with fever and hyperleukocytosis
    - Subject will be prescribed appropriate therapy depending on type and severity of symptoms
  - Angioedema
    - Treatment will depend on the severity. If severe, Subject will be referred to the hospital for evaluation and treatment. If less, severe may be treated with antihistamines, anti-

inflammatories, or glucocorticoids.

- Gastrointestinal
  - Abdominal pain
    - Subject will be medically managed. If severe treatment may be discontinued.
  - Nausea
    - Subject will be prescribed anti-nausea medication if needed
  - Loose Stools & Diarrhea
    - Subject will be prescribed anti-diarrheal medication if needed
  - Vomiting
    - Subject will be prescribed anti-emetic medication if needed
  - Flatulence
    - Subject will be advised to try over-the-counter anti-flatulence medication if needed
  - Dyspepsia
    - Subject will be prescribed appropriate therapy such as an H2 receptor antagonist or PPI if needed
  - Stomatitis
    - If needed Subject will be advised to:
      - Avoid hot beverages and foods as well as salty, spicy, and citrus-based foods.
      - Use pain relievers like Tylenol or ibuprofen.
      - Gargle with cool water or suck on ice pops if they have a mouth burn.
  - Gastroenteritis
    - Subject will be prescribed appropriate therapy if needed
  - Oral candidiasis
    - Subject will be prescribed appropriate antifungal medications if needed
  - Constipation
    - Subject will be prescribed stool softening medication if needed
  - Dysphagia/ oral dysphagia
    - Depending on the severity Subject might be managed with medication such as PPI
  - Abdominal distention
    - Subject will be medically managed. If severe Subject will have teleconference with PI and may be referred for in-person visit with PI and/or hospitalization.
  - Dry mouth
    - Subject will be advised to drink water and chew gum
  - Eructation
    - Subject will be advised to eat and drink slowly and avoid carbonated beverages. If this does not work, PPI may be prescribed if needed
  - Mouth ulceration
    - If mild Subject will be advised to:
      - Avoid hot beverages and foods as well as salty, spicy, and citrus-based foods.
      - Use pain relievers like Tylenol or ibuprofen.
      - Gargle with cool water or suck on ice pops if they have a mouth burn.
    - If moderate or severe Subject will be medically managed
  - Salivary hypersecretion
    - Should resolve when treatment is completed
  - Pseudomembranous colitis
    - Subject will be medically managed
  - Pancreatitis
    - Subject will be referred for hospital for evaluation

- Tongue discoloration
  - Will be monitored
- Melena
  - Medical management will be utilized first if needed. If this is unsuccessful, Subjects will be evaluated and treated based on current standards of care
- Enteritis
  - Will be symptomatically managed. If symptoms persist, Subject may be referred for hospitalization
- Abnormal stools
  - Subject will be medically managed
- Gastrointestinal dysfunction
  - Subject will be symptomatically managed
- Pyloric stenosis
  - Subject will be referred to PCP for evaluation and standard of care therapy
- Genitourinary
  - Vaginitis/Vaginal infection
    - Subject will be prescribed appropriate antibiotic or antifungal therapy
  - Dysuria
    - Urinalysis will be performed to check for bladder infection. If one is found it will be treated with appropriate antibiotics. If UTI is not found, diagnostics such as vaginal/urethral culture will be run to test for other causes. If these are found, they will be medically managed.
  - Intermenstrual bleeding
    - Subjects will be advised that this should end once treatment is completed. Subject will be referred to a gynecologist if needed.
  - Testicular disorder
    - Subject will be referred to a specialist
- Hematologic
  - Any hematological abnormalities found during treatment or after will be followed by subsequent CBCs. If the problem is severe, Subject may be medically managed or referred for hematology consultation and possible hospitalization.
- Hepatic
  - Hepatitis
    - Medication will be discontinued, and Subject will be monitored. If liver values do not return to normal Subject will be referred to a specialist
  - Elevated AST, ALT, GGT, and/or bilirubin
    - Follow-up metabolic panels will be run. Subjects will be advised to refrain from drinking alcohol for the duration of the trial. If values do not return to normal, Subject will be referred to their PCP or GI specialist
  - Hepatic failure/fulminant hepatic failure/fulminant hepatitis/hepatic necrosis
    - Subject will be referred for hospitalization
- Hypersensitivity
  - Allergic reaction/hypersensitivity
    - Subject will be medically managed with antihistamines and standard-of-care
  - Angioedema
    - Subject's airway will be managed. Subject will be treated with antihistamines and if necessary, glucocorticoids.
  - Anaphylactic reaction
    - Subject will be emergently treated with epinephrine and referred for hospitalization if necessary

- Immunologic
  - Moniliasis
    - Subject will be treated with appropriate antifungal therapy.
  - Flu syndrome
    - Subject will be tested for influenza. If positive, Subject will be prescribed appropriate antiviral regimen
- Metabolic
  - Abnormal blood chemistry values including below will be monitored. If they do not return to normal Subject will be treated accordingly
    - Decreased bicarbonate
    - Hyponatremia
    - Elevated alkaline phosphatase
    - Elevated bicarbonate
    - Hyperchloridemia
    - Elevated lactate dehydrogenase
    - hyponatremia
    - Hypokalemia
    - Decreased copper absorption
  - Dehydration
    - Subject will be advised to increase fluids and possibly electrolyte intake. If this does not solve the problem, or it is severe, Subject may be referred for hospitalization
  - Anorexia
    - Subject will be monitored for resolution of symptoms. If they do not resolve on their own, Subject will be medically managed
- Musculoskeletal
  - Sensorimotor disorders
    - Subject will be referred to a specialist
  - Skeletal muscle myopathy or neuromyopathy
    - May be reversible by stopping medication but recovery can take months. Subject will be referred to a specialist
  - Depression of tendon reflexes/ Abnormal nerve conduction studies
    - Subject will be referred to a specialist
  - Arthralgia/myalgia/neck pain/back pain
    - Subject will be medically managed
  - Osteoarthritis
    - Subject will be medically managed. If the condition worsens Subject will be referred to a specialist
  - Elevated creatine kinase
    - Subject will be monitored. If condition persists or worsens, Subject will be referred to a specialist
- Nervous system
  - Headache/dizziness/vertigo
    - Subject will be medically managed
  - Seizure
    - Subject will be referred to a neurologist for diagnostics and treatment
  - Ataxia
    - Subject will be referred to a neurologist for diagnostics and treatment
  - Auditory nerve dysfunction
    - Subject will be referred to a specialist for evaluation and treatment

- Optical
  - Blurred vision
    - Dose dependent and reversible upon discontinuation of medication
    - Medication will be discontinued
  - Retinopathy with changes in pigmentation and visual field defects
    - Subjects with retinal changes may be asymptomatic initially, or may have scotomatous vision with paracentral, pericentral ring types, temporal scotomas, and abnormal color vision.
    - Subjects will be referred to an ophthalmologist
  - Corneal changes including edema and opacities can be symptomless or may cause disturbances such as haloes, blurring of vision or photophobia. They may be transient and are reversible when therapy is discontinued.
    - Therapy will be discontinued
  - Maculopathies and macular degeneration (may be irreversible), extra-ocular muscle palsies (reversible), nystagmus
    - Maculopathies and macular degeneration can occur from 3 months to several years of exposure to this drug and may be irreversible
    - Treatment will be discontinued, and Subject will be referred to an ophthalmologist
- Other
  - Fatigue/Aesthenia/Malaise/fever/chills
    - Subject will be monitored. If this does not resolve with treatment Subject will undergo further diagnostics to determine the etiology
  - Candidiasis
    - Subject will be treated with appropriate antifungal therapy
  - Ear disorder
    - Subject will be referred to a specialist
  - Face edema
    - Subject will have bloodwork and urinalysis done. Depending on findings Subject may be medically managed or referred to a specialist and treatment discontinued.
  - Pain
    - Subject will be medically managed
  - Post-procedural complications
    -
  - Fungal or bacterial infection
    - Subject will be treated with appropriate antimicrobial therapy
  - Mucositis
    - Should resolve with completion of treatment. Will be medically and symptomatically managed
- Psychiatric
  - Affect lability
    - Subject will be referred to a specialist
  - Nervousness
    - Subject will be referred to a specialist
  - Psychosis
    - Subject will be referred to a specialist
  - Suicidal behavior
    - Subject will be referred to a specialist
  - Insomnia
    - Subject will be medically managed. If this fails Subject will be referred to a specialist

- Agitation
  - Subject will be referred to a specialist
- Aggression
  - Subject will be referred to a specialist
- Anxiety
  - Subject will be referred to a specialist
- Delirium
  - Subject will be referred to a specialist, possibly for hospitalization
- Hallucination
  - Subject will be referred to a specialist, possibly for hospitalization
- Irritability
  - Subject will be referred to a specialist
- Hostility
  - Subject will be referred to a specialist
- Renal
  - Renal pain
    - Subject will be medically managed
  - Increased BUN and creatinine
    - Subsequent labs will be run. If the values do not return to normal treatment will be discontinued. Will be followed until values return to normal.
  - Acute renal failure
    - Treatment will be discontinued. Subject will be referred for hospitalization
  - Interstitial nephritis
    - CBC will be run to determine if there is an infectious etiology. Treatment will be discontinued. Subject will be treated with corticosteroids.
- Respiratory
  - Dyspnea/pneumonia/pleural effusion
    - Subject will be referred for hospitalization
  - Pharyngitis
    - Subject will be given a rapid strep test and if this is positive will be treated with appropriate antibiotics. If negative Subject will be symptomatically medically managed
  - Rhinitis
    - Subject will be medically managed
  - Respiratory disorder
    - Subject will undergo clinical evaluation to determine the nature of the disorder. If determined to be other than COVID-19 will be medically managed
  - Epistaxis
    - Subject will apply pressure to the nasal alae for at least 10 minutes or until bleeding stops. If severe Subject will be evaluated for blood loss and possibly be referred for hospitalization
  - Bronchospasm
    - Treatment will be discontinued, and Subject will be treated with antihistamines
  - Cough
    - Subject will be advised to use lozenges. If the symptom is severe, cough syrup may be prescribed
  - Asthma
    - Treatment will be discontinued, and Subject will be given supportive care
    - Bronchitis Subject will be medically managed with supportive treatment.

#### 20.4 Appendix 4: Subject Stopping Criteria

- QT interval >500msec
- Increase in QT >30-60msec
- Presence of torsades de pointes
- Occurrence of unexpected drug related SAE
- Any other risk which the Investigator deems necessary to discontinue the study drugs

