**Duration of Subject Participation (Study Visits)**

Subjects will be given the opportunity once diagnosis has been made via RT-PCR testing to participate. They may be recruited through the ProgenaBiome website, through a questionnaire. They may also be recruited through [www.clinicaltrials.gov](http://www.clinicaltrials.gov). Subjects may be referred by healthcare facilities. Subjects may also self-refer as well. All potential Subjects will be called during the recruitment process for screening assessments. The first step of this will be to obtain informed consent electronically, via the EDC. We will attempt to connect with these Subjects via Zoom/telemedicine. The validity of the test used to diagnose will be verified through medical records. (The diagnosis will be made by the Subject's evaluating physician or evaluation testing center, as part of the standard of care when infection is suspected). Following successful screening, Subjects will be randomized into the Arm 1 (treatment) or Arm 2 (placebo). At this time the associated treatment regimen will be prescribed and shipped to the Subject's home, along with home health equipment (MoMe Kardia II, thermometer, pulse oximeter and pregnancy test). Subjects will take azithromycin for 5 days, and hydroxychloroquine for 10 days, along with vitamin C, vitamin D, and zinc. Starting at Day 11 Subjects will discontinue hydroxychloroquine and reduce the doses of vitamin C, vitamin D, and zinc. The vitamin C, D, and zinc will be taken an additional 20 days at the reduced dose. Subjects will use the home EKG to transmit heart function information to the Study Team to be read by a board-certified cardiologist prior to dosing. The EKG will then be used daily for 10 days and results transmitted to the study team. Subjects will use a home pulse oximeter to monitor oxygen saturation and photographically report these values to the study team via the EDC. Subjects will track their symptoms using a daily diary (provided). Subjects will collect nasal or oropharyngeal swabs on Days 3, 5, 7, 14, and Month 1 and Month 3 for RT-PCR testing. Once Subjects have tested negative following treatment with HAZDpaC, Subjects will present to the clinic at 1, 2, and 3 months post-treatment for viral testing via RT-PCR. Alternatively, these visits may be conducted via videoconference and the subjects may collect these samples at home. At these visits blood will be drawn, a physical exam performed, and vital signs measured (optional). At the month 3 visit a pregnancy test will be given if applicable. Should Subject remain symptomatic at 2 weeks, or return to a positive state at any time during the trial they will be referred to their PCP by a phone call directly from the PI to the PCP. If at any time during the treatment phase or subsequent follow up Subject expresses and demonstrates a worsening or persistence of symptoms, they will be cared for according to standard of care or referred to their primary care provider, according to patient preference. The PI will discuss the case directly with that primary care provider. Subjects will continue to be followed for the remainder of the trial, and documentation of any additional treatments and Subject outcomes will be collected.

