## 3. Study Procedures:

- Diagnosis, Medical Review, and Prescription of Therapy (Screening, Day -3 to Day -1):
  - Subject will provide electronic informed consent via the EDC portal.
  - Medical Information
    - a. Study staff will review prior and concomitant medications, including over-the-counter medications and supplements.
    - b. Investigator will review the Subject's records during the screening process, looking at inclusion/exclusion criteria, gathering data on vital signs, EKG recordings, and oxygen saturation. These values will be used to compare to values obtained throughout the study. If any contraindication to participation is found, the study drugs will not be provided and the subject will be deemed a screen failure.
  - Diagnosis of COVID-19 will be confirmed
    - a. May be based on PCR testing results, rapid antigen testing results, or clinical presentation at screening as assessed by the Principal Investigator including symptoms such as:
      - Fever
      - Cough
      - Anosmia
  - Subject will be provided a daily diary for recording symptoms.
  - Subject will be randomized into Arm 1 or Arm 2
  - Prescription of treatment drugs
    - a. Arm 1: Medications will be prescribed for Quintuple Therapy
      - Hydroxychloroquine 200MG BID for 10 days, Azithromycin 500mg on day 1, 250mg day 2-5, Vitamin C 3000mg for 10 days, then 1500mg for 20 days, Vitamin D 3000IU for 10 days, then 1500IU for 20 days, and zinc 50mg for 10 days, then 25mg for 20 days.
    - b. Arm 2: Placebos and supplements will be provided (to ensure nutritional parity)
      - Placebo for Hydroxychloroquine BID for 10 days, Placebo for Azithromycin to be taken 2 the on Day 1, then 1 on Days 2-5, Vitamin C 3000mg for 10 days, then 1500mg for 20 days, Vitamin D 3000IU for 10 days, then 1500IU for 20 days, and zinc 50mg for 10 days, then 25mg for 20 days.
    - c. Drugs shall be taken first thing in the morning as soon as the patient has eaten. Vitamins will be taken with lunch and dinner, and then the evening dose of drugs will be right before bed.
  - Monitoring equipment provided
    - a. Home EKG recording device

- b. Pulse Oximeter
    - c. Thermometer
    - d. Urine Pregnancy test if applicable
  - Subject will be isolated as an outpatient
    - a. All CDC recommendations regarding self-quarantine must be followed
- Treatment Period
  - Day 1 following positive test (isolation)

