    - a. Subject will be video called to ensure they have all study materials and go over:
      - Use of home health equipment
        - Subject will take baseline measurements at this time and record it in the diary
      - Diary and how to transmit its contents
      - Medication dosing
    - b. Subject will take pregnancy test if applicable
    - c. Subject will use provided equipment to measure vital signs
      - EKG
      - Oxygen Saturation
      - Temperature
    - d. Subject will take prescribed regimen

Drug	AM Dose	PM Dose
Hydroxychloroquine (or Placebo)	200mg	200mg
Azithromycin (or Placebo)	500mg	---
Vitamin C	1500mg	1500mg
Vitamin D	1500IU	1500IU
Zinc	25mg	25mg

- Hydroxychloroquine and azithromycin will be taken early in the morning with breakfast and right before bed. Vitamins and Zinc will be taken with lunch and dinner
  - Day 2
    - a. Subject will complete AM and PM diaries
    - b. Subject will use provided equipment to measure vital signs
      - EKG
      - Oxygen saturation
      - Temperature
    - c. Subject will take prescribed regimen

Drug	AM Dose	PM Dose
Hydroxychloroquine (or Placebo)	200mg	200mg
Azithromycin (or Placebo)	250mg	---
Vitamin C	1500mg	1500mg
Vitamin D	1500IU	1500IU
Zinc	25mg	25mg

- Day 3
    - a. Subject will be called
      - Ask if they are experiencing any difficulties with swab collection
      - Ask about AE/SAE
      - Update list of prior and concomitant medications
      - Ask about symptom resolution or progression

- Instruct how to collect nasal or oropharyngeal swabs
  - Subject will collect first nasal or oropharyngeal swab
- Answer any questions the Subject may have
- b. Subject will complete AM/PM diaries
- c. Subject will use provided equipment to collect vital signs
  - EKG
  - Oxygen saturation
  - Temperature
- d. Subject will take prescribed regimen

Drug	AM Dose	PM Dose
Hydroxychloroquine (or Placebo)	200mg	200mg
Azithromycin (or Placebo)	250mg	---
Vitamin C	1500mg	1500mg
Vitamin D	1500IU	1500IU
Zinc	25mg	25mg

○ Day 4

- a. Subject will complete AM/PM diaries
- b. Subject will use provided equipment to collect vital signs
  - EKG
  - Oxygen saturation
  - Temperature
- c. Subject will take prescribed regimen

Drug	AM Dose	PM Dose
Hydroxychloroquine (or Placebo)	200mg	200mg
Azithromycin (or Placebo)	250mg	---
Vitamin C	1500mg	1500mg
Vitamin D	1500IU	1500IU
Zinc	25mg	25mg

○ Day 5

- a. Subject will complete AM/PM diaries
- b. Subject will be called
  - remind them to collect swab

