- e. To include EKG, oxygen saturation, and temperature
- f. Vitals in-clinic to include height (only at first visit), weight, blood pressure (following 5 minutes sitting) pulse, respiratory rate, temperature, and oxygen saturation (Optional)
- g. To include CBC, Complete Metabolic Panel, and CRP (details in section 9 Sample Collection) (Optional)

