### **13. Risk/Benefit Assessment**

#### **13.1 Potential Risks**

- Confidentiality Risks: All data (clinical, demographic, etc.) for individual subjects will be provided to ProgenaBiome. Information obtained during the study will not be shared outside the study personnel except in scientific reports or publications in aggregated and deidentified form.

- Risks associated with Hydroxychloroquine
  - Auditory
    - Tinnitus
    - Hearing loss
  - Cardiovascular
    - Cardiomyopathy (can result in fatal cardiac failure)
    - biventricular hypertrophy
    - Prolongation of Q-T Interval
  - Dermatologic
    - Pigmentary changes in skin and mucous membranes
      - Usually reversible upon discontinuation of medication
    - Bleaching of hair
      - Usually reversible upon discontinuation of medication
    - Alopecia
      - Usually reversible upon discontinuation of medication
    - Rash/pruritus
    - AGEP
      - Usually reversible upon discontinuation of medication
    - Outbreak of psoriasis, occasionally associated with fever and hyperleukocytosis
    - Urticaria
    - Angioedema
    - Bullous eruptions including
      - Erythema multiforme
      - Stevens-Johnson syndrome
      - Toxic epidermal necrolysis
    - DRESS syndrome
    - Photosensitivity
    - Exfoliative dermatitis
  - Gastrointestinal
    - Abdominal pain
    - Nausea
    - Diarrhea
    - Vomiting
  - Hematologic
    - Bone marrow suppression
    - Anemia
    - Aplastic anemia
    - Agranulocytosis
    - Leukopenia
    - Thrombocytopenia
  - Hepatic
    - Fulminant hepatic failure
  - Metabolic
    - Anorexia
    - Hypoglycemia
    - Exacerbation or precipitation of porphyria
  - Musculoskeletal
    - Sensorimotor dysfunction
    - Skeletal muscle myopathy or neuromyopathy

- May be reversible by stopping medication but recovery could take months
  - Depression of tendon reflexes
  - Abnormal nerve conduction studies
- Nervous system
  - Headache
  - Dizziness
  - Seizure
  - Vertigo
  - Auditory nerve dysfunction
  - Ataxia
- Optical
  - Blurred vision
    - Dose dependent and reversible upon discontinuation of medication
  - Retinopathy with changes in pigmentation and other visual field defects
    - Subjects with retinal changes may be asymptomatic initially, or may have scotomatous vision with paracentral, pericentral ring types, temporal scotomas, and abnormal color vision.

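### Appendix 4's QT stopping rules specify no heart-rate correction, give the rise limit as a range, and do not say which EKG is the reference

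*Combined protocol and SAP*

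**What the plan says.** Appendix 4 (Subject Stopping Criteria) has two numerical QT lines: "QT interval >500msec" and "Increase in QT >30-60msec". The other entries are torsades de pointes, an unexpected drug-related SAE, and any further risk that the investigator judges sufficient.

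The monitoring behind these lines is in three places.
- The synopsis has a home EKG "to be read by a board-certified cardiologist prior to dosing", and then: "The EKG will then be used daily for 10 days and results transmitted to the study team".
- Section 3 schedules an EKG on each of Days 1 to 10. Footnote e to the Schedule of Events (Section 6) defines the home vitals: "To include EKG, oxygen saturation, and temperature". Footnote b says that the EKG device is worn continuously.
- Two texts could supply a reference. At screening, Section 3 says of the vital signs, EKG recordings and oxygen saturation: "These values will be used to compare to values obtained throughout the study". On Day 1 it says: "Subject will take baseline measurements at this time and record it in the diary".

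Section 13.1 lists "Prolongation of Q-T Interval" among the cardiovascular risks of hydroxychloroquine. The exclusion criteria, in the synopsis and in Section 3, also use plain QT: a history above 500 msec, and an unquantified QT prolongation on EKG. No section mentions a corrected QT or a correction formula.

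**The concern.** The QT interval lengthens as the heart slows and shortens as it speeds up, with or without drug. A rule on uncorrected QT therefore responds to rate as well as to repolarisation. Fever is one of the presenting symptoms named in Section 3, so a subject may start with a raised rate that falls with recovery. A literal reading could then stop drug in either arm without any QT effect, and in Arm 1 cut short the 10-day hydroxychloroquine course under test. If the rate rises instead, real prolongation can go unflagged.

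The range adds a second problem: two readers can act differently on the same tracing. The unnamed reference adds a third.

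The rule carries weight because subjects are isolated outpatients, and Appendix 3 (Mitigation of Side Effects) has no cardiovascular heading. Appendix 4 is where the plan says what to do about a long QT on treatment.

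**Working it through.** **Text check.** A rise of 45 msec exceeds 30 and does not exceed 60, so the rise line gives no single answer between 31 and 60 msec. The 500 msec line does have one limit. For the reference, Section 3 offers screening values and Day 1 values, and the synopsis offers a pre-dose EKG read by a cardiologist. Some of these may be the same tracing. Appendix 4 points to none of them.

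**Inputs.** From the documents: the limits 500, 30 and 60 msec. Assumed, because the documents give neither: corrected QT (QTc) of 400 to 440 msec, and the heart rates (HR) below. The plan has no figure of its own to reproduce here.

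**Formula.** Raw QT = QTc × (60/HR)^p, with p = 1/3 (cube-root) or p = 1/2 (square-root).

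**1. Slowing from 90 to 60 bpm, no drug effect.** Change = QTc × [1 − (60/90)^p].
- Cube-root: (2/3)^(1/3) = 0.8736. 400 × 0.1264 = 50.6; 440 × 0.1264 = 55.6 msec.
- Square-root: (2/3)^(1/2) = 0.8165. 400 × 0.1835 = 73.4; 440 × 0.1835 = 80.7 msec.
- Two linear formulas agree with the lower figures: Framingham, 154 × (1 − 60/90) = 51.3; Hodges, 1.75 × 30 = 52.5 msec.

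All exceed 30 msec. Only the square-root result exceeds 60. A 30 msec rise is already reached on slowing from 90 to 70.3-71.8 bpm (cube-root) or 75.5-76.7 bpm (square-root).

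**2. True QTc rise of 60 msec while the rate goes from 70 to 90 bpm.** Change = (QTc + 60) × (60/90)^p − QTc × (60/70)^p.
- Cube-root: 460 × 0.8736 − 400 × 0.9499 = 21.9; 500 × 0.8736 − 440 × 0.9499 = 18.8 msec.
- Square-root: 460 × 0.8165 − 400 × 0.9258 = 5.3; 500 × 0.8165 − 440 × 0.9258 = 0.9 msec.

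The true rise reads below even the 30 msec end.

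**3. The 500 msec line.** QTc equivalent = 500 × (HR/60)^p. At 100 bpm: 592.8 (cube-root) or 645.5 (square-root). At 50 bpm: 470.5 or 456.4. One raw limit thus corresponds to quite different corrected values.

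**4. What cube-root correction leaves.** If the cube-root relation is true, the shift in step 1 becomes zero. If the square-root relation is true, the residual is QTc × [1 − (60/HR)^(1/6)] on slowing to 60 bpm.
- From 90 bpm: 400 × 0.0653 = 26.1; 440 × 0.0653 = 28.8; at QTc 460, 30.1 msec.
- From 100 bpm: 400 × 0.0816 = 32.6; 440 × 0.0816 = 35.9 msec.

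In the other direction, under the same mismatch, the true 60 msec rise in step 2 would read as (QTc + 60) × (2/3)^(1/6) − QTc × (6/7)^(1/6): 460 × 0.93466 − 400 × 0.97464 = 40.1, and 500 × 0.93466 − 440 × 0.97464 = 38.5 msec. That is above 30 and below 60. Correction helps in both directions but does not remove all rate dependence.

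**The case against.** The strongest reply is that Appendix 4 says QT, not uncorrected QT. The protocol uses the plain term throughout, a cardiologist is involved, and a cardiologist may correct as a matter of course. That stands as far as it goes: a reader might infer that the plan mandates raw QT, and the documents do not support that. They leave the correction unspecified. But no correction is instructed anywhere. The only cardiologist read that is specified precedes dosing; later results go to the study team. It would be equally unsupported to infer that no cardiologist sees those later tracings.

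Second, the sizes rest on assumed inputs, and if 60 msec governs, most of the 90-to-60 bpm illustration gives no stop. Both are true. It follows that slowing alone *can* trigger the rule, not that it will.

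Third, the documents suggest a reason for rates to fall (fever settling), which errs towards caution, and none for rates to rise. So the missed-prolongation case is a possibility without a documented mechanism, and neither direction has a known frequency.

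Fourth, investigator discretion is a safeguard. It can add a stop, though only if someone sees prolongation that the raw number hides. It does not cancel a stop that a listed criterion requires.

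Finally, a reader might infer that there is no reference EKG at all, or that the rule distorts the treatment comparison. Section 3 gives two candidate references, so the gap is in Appendix 4's failure to choose. Nothing in the documents allows an effect on efficacy to be shown.

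**Conclusion.** The point holds as a defect in a safety rule. Three wording facts need no assumption: no rate correction is specified, the rise limit is a range, and the reference EKG is not identified. The consequence is that, followed as written, the rule can stop drug on rate change alone or miss true prolongation.

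The sizes are illustrative and depend on an assumed corrected QT of 400-440 msec and the chosen heart rates. False signal: 51-56 or 73-81 msec for 90 to 60 bpm. Masked signal: a true 60 msec rise seen as about 1 to 22 msec for 70 to 90 bpm. How many subjects would be affected is unknown. This should be corrected before use because the rule protects participants and the change is small.

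**What to change.** Replace the two QT lines in Appendix 4 with:
- Rate-corrected QT (cube-root: QT/(60/HR)^(1/3)) >500 msec.
- Increase in rate-corrected QT (same formula) above one stated limit over the pre-dose EKG read by the cardiologist, assessed on every post-dose EKG from Day 1 through Day 10.

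The cardiologist picks one limit, 30 or 60 msec. The 60 msec limit tolerates residual rate dependence better; 30 is more protective. Day 1 after dosing should stay in: it is the 500 mg azithromycin day, and a device worn continuously can supply the recording.

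Use the same corrected definition for the QT exclusion criteria in the synopsis and in Section 3, so that entry and stopping use one measure.

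Cost: heart rate and one calculation per EKG. The present rule already needs a QT value, but Appendix 1 lists no QT output for the device, so QT may have to be measured by hand. Some rate dependence remains: about 26-36 msec for slowing from 90-100 to 60 bpm if the square-root relation is true, at corrected QT 400-440 msec. No new visits are needed.
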